12.3.2.2 Methods of Analysis

Summaries of the number and percent of subjects with at least one SAE will be provided. Comparisons of the proportion of subjects experiencing SAEs will be made between treatment arms. Summaries of the number of percent of AEs will be provided for each treatment arm.

Differences in mean overall blood loss, mean volume of intra-operative transfusions, mean total operative time, and mean duration of hospitalization will be estimated using linear regression models with stratified adjustment for surgery type and separated by surgery type. In all cases, the robust variance estimator will be used and a 95% Wald-based interval will be computed. Comparisons of the incidence of re-operation (total and reoperation due to bleeding) and the incidence post-surgery bleeding complications will be made using a general linear model to estimate the difference in the probability of each outcome after stratified adjustment for surgery type. Comparisons of the incidence of re-operation and the incidence post-surgery bleeding complications within each surgery type will be made using a two sample binomial test of proportions.

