5.4 Additional Exploratory Outcomes

The additional exploratory outcomes of this clinical investigation that will be described and quantified are:

- Operative time for HEMOBLAST™ subjects compared to G+T subjects;
- Duration of hospitalization for HEMOBLAST™ subjects compared to G+T subjects; and
- Number of units of blood transfused intraoperatively for HEMOBLAST™ subjects compared to G+T subjects.

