6.4 Intraoperative Procedures and Evaluations

All subjects will undergo the same intraoperative investigational evaluations. Intraoperative is defined as the time interval from when the subject enters the surgical suite until the subject exits the surgical suite.

Subjects undergoing the open elective cardiothoracic, abdominal, and orthopedic lower extremity surgeries are eligible for enrollment into the clinical investigation. The Investigator will perform the surgery per his or her standard procedures, including conventional methods of hemostasis (pressure, ligation, cautery, etc.).

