6.4.2 Randomization and Hemostat Application

At the start of each surgical procedure, a single HEMOBLAST™ device and a single G+T device will both be prepared per the respective Instructions for Use (unless the subject is a lead-in subject; all lead-in subjects will have a single HEMOBLAST™ device prepared). The preparation time for both devices will be recorded for the TTH Population subjects.

Randomization will be performed through sequentially numbered sealed envelopes. Four-hundred subjects (TTH Population) will be randomized to receive HEMOBLAST™ or G+T in a 2:1 ratio:

- 267 subjects will be randomized to receive HEMOBLAST™; and
- 133 subjects will be randomized to receive G+T.

There will be a maximum of 50 lead-in subjects; these subjects will not be randomized. The first subject for each investigator will be treated as a lead-in subject. These subjects will receive HEMOBLAST™ and will be followed for safety only (maximum Full Analysis Population of 450); lead-in subjects will not count towards the TTH Population. Please see Section 12 below for additional detail on subject populations.

Randomization will be stratified by surgical indication and will incorporate blocking; additional details of randomization and blocking will be included in a separate Randomization Plan.

After randomization and enrollment, the assigned hemostat will be used in the investigational subject; the other hemostat will be discarded following institutional procedures.

A study-specific stopwatch will be used to track hemostat application and the times of hemostasis evaluation. The time of initial hemostat application will be considered time 0; at this time, the stopwatch will be started by the study coordinator. The stopwatch will run continuously without stopping.

Hemostasis will be evaluated by the investigator at the following time points until hemostasis has been achieved:

- 3 minutes;
- 6 minutes; and
- 10 minutes.

Reapplication of the randomized hemostat will be performed at the 3 minute and 6 minute evaluation time points, as described below.

For cardiothoracic procedures, the TBS will be identified after heparin reversal. Additionally, the TBS will not be at the site of a valve implant or at the site of a synthetic graft or patch implant.

HEMOBLAST™ will be applied according to its instructions for use.

1. Peel open the pouches to remove contents with attention to sterile procedures.
2. Remove cap using a twisting motion.

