6.4.5 Intraoperative Data Collection

The following data will be recorded on the Intraoperative CRF:

- Surgical procedure(s);
- Preparation times for each device;
- Description of TBS;
 - Location,
 - Tissue type,
 - Conventional means for hemostasis (pressure, suture, cautery, etc.),
- Confirmation of intraoperative eligibility criteria;
- Approximate dimensions of target bleeding site;
- SBSS score at baseline and each evaluation time point (3, 6, and/or 10 minutes) until hemostasis is achieved;
- Randomization;
 - Randomization envelope number,
 - Time of randomization,
 - Treatment arm and device lot/batch number data,
- Hemostat application;
 - Application amount
 - HEMOBLAST™ application amount will be approximated by indicating the amount of powder left in the bellows after application
 - G+T application amount will be documented by approximating the dimensions of Surgifoam sponge applied
- Rescue treatment(s), if any;
- Use of other hemostatic agent(s), if any;
- Skin open and skin closure times;
- Intraoperative administration of blood products;
- Total intraoperative estimated blood loss;
- Incidence of any device deficiencies; and

- Incidence of any complications or adverse events.

The Concomitant Medication, Adverse Event, and Device Deficiency CRFs will be completed as applicable.

Table 7 below shows a timeline of intraoperative procedures.

Table 7. Timeline for Intraoperative Procedures*

Time Point (Minutes:Seconds)	Study Procedures or Assessments
Prior to 00:00	
 • Prepare both hemostatic devices and record time of preparation • Identify Target Bleeding Site (TBS) • Assign SBSS score • Perform randomization (unless lead-in subject)
00:00	
 • Start stop-watch • Apply HEMOBLAST™ or G+T
03:00	
 • Assign SBSS score 
If SBSS = 0
 
 • Intraoperative efficacy evaluation completed 
If SBSS is NOT 0
 
 • Re-apply HEMOBLAST™ or G+T
06:00	
 • Assign SBSS score 
If SBSS = 0
 
 • Intraoperative efficacy evaluation completed 
If SBSS is NOT 0
 
 • Re-apply HEMOBLAST™ or G+T

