Intraoperative Time	Time from skin open to skin closure
IRB	Institutional Review Board
QA	Quality Assurance
Relationship (of an adverse event to the investigational device)	
 • Not related: the adverse event is due to the underlying disease state or is due to concomitant medications or therapy not related to the use of the device • Possibly related: the adverse event has a reasonable temporal relationship to the use of the device but alternative etiology is equally or more likely compared to the potential relationship to the use of the device • Probably related: the adverse event has a strong temporal relationship to the use of the device and alternative etiology is less likely compared to the potential relationship to the use of the device • Definitely related: the adverse event has a strong temporal relationship to the use of the device, follows a known response pattern and cannot reasonably be explained by known characteristics of the subject's clinical state or other therapies
SADE	Serious Adverse Device Effect – an adverse device effect that has resulted in any of the consequences characteristic of a serious adverse event or that might have led to any of these consequences if suitable action had not been taken or intervention had not been made or if circumstances had been less opportune
SAE	Serious Adverse Event – an adverse event that: 
 • Led to death • Led to a serious deterioration in the health of the subject, that either resulted in a life-threatening illness or injury, or a permanent impairment of a body structure or a body function, or in-patient hospitalization or prolongation of existing hospitalization, or resulted in medical or surgical intervention to prevent life-threatening illness or injury or permanent impairment to a body structure or a body function •
SBSS	Surface Bleeding Severity Scale

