8.2 Randomization

At the start of each surgical procedure, a single HEMOBLAST™ device and a single G+T device will both be prepared per the respective Instructions for Use (unless the subject is a lead-in subject; all lead-in subjects will have a single HEMOBLAST™ device prepared). The preparation time for both devices will be recorded for the TTH Population subjects.

Randomization will be performed just prior to treatment through sequentially numbered sealed envelopes. Four-hundred subjects (TTH Population) will be randomized to receive HEMOBLAST™ or G+T in a 2:1 ratio:

- 267 subjects will be randomized to receive HEMOBLAST™; and
- 133 subjects will be randomized to receive G+T.

There will be a maximum of 50 lead-in subjects; these subjects will not be randomized. The first subject for each investigator will be treated as a lead-in subject. These subjects will receive HEMOBLAST™ and will be followed for safety only (maximum Full Analysis Population of 450); lead-in subjects will not count towards the TTH Population. Please see Section 12 below for additional detail on subject populations.

Randomization will be stratified by site and will incorporate random permuted blocking; additional details of randomization and blocking will be included in a separate Randomization Plan.

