10.6.2 Analytic Methods

Endpoints used to characterize the safety profile include the rate of occurrence of all AEs and SAEs, reoperation rate due to bleeding, mean volume of intraoperative transfusions, total operative time, mean

duration of hospitalization, intraoperative blood product administration, and post-operative blood product administration.

Summaries of the number and percent of subjects with at least one SAE will be provided. Comparisons of the proportion of subjects experiencing SAEs will be made between treatment arms. Summaries of the number of percent of AEs will also be provided for each treatment arm.

Differences in mean overall blood loss, mean volume of intra-operative transfusions, mean total operative time, and mean duration of hospitalization will be estimated using linear regression models with stratified adjustment for surgery type and separated by surgery type. In all cases, the robust variance estimator will be used and a 95% Wald-based interval will be computed. Comparisons of the incidence of re-operation (total and reoperation due to bleeding) and the incidence post-surgery bleeding complications will be made using a general linear model to estimate the difference in the probability of each outcome after stratified adjustment for surgery type. Comparisons of the incidence of re-operation and the incidence post-surgery bleeding complications within each surgery type will be made using an exact two sample binomial test of proportions.

For binary endpoints, the proportion and corresponding 95% scored-based confidence interval will be computed. The proportion of UADEs or SADEs will also be computed and a 95% scored-based confidence interval will be computed for the true UADE or SADE rate. In the event that no UADEs or SADEs are observed, the upper bound of the 95% confidence interval will be based upon the exact binomial distribution.

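### The operative-time comparison includes time before randomisation, which costs precision; randomisation-to-closure time can be derived from the CRF but is not analysed

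*Protocol*

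**What the plan says.** - **The comparison.** Operative time is a safety outcome in Protocol 12.1.3 and in SAP 10.6.2, which lists "reoperation rate due to bleeding, mean volume of intraoperative transfusions, total operative time, mean" duration of hospitalization. It is also an exploratory outcome in Protocol 5.4 and SAP 10.8: "Operative time for HEMOBLAST™ subjects compared to G+T subjects". Protocol 12.3.2.2 gives the method: differences in "mean total operative time, and mean duration of hospitalization will be estimated using linear regression models", with surgery type as the only adjustment, a robust variance and a 95% Wald interval.
- **When assignment happens.** Protocol 6.4.1 randomises a subject only after the intraoperative criteria are met, including a bleeding site for which conventional means do not serve. Protocol 6.4.2 places site identification after heparin reversal in cardiothoracic cases. SAP 8.2 says: "Randomization will be performed just prior to treatment through sequentially numbered sealed envelopes".
- **What is recorded.** The Intraoperative CRF (Protocol 6.4.5) holds the time of randomisation and also "Skin open and skin closure times".
- **Definitions.** Total operative time is not defined. Protocol 17 defines the term Intraoperative Time as "Time from skin open to skin closure", while Protocol 6.4 says: "Intraoperative is defined as the time interval from when the subject enters the surgical suite until the subject exits the surgical suite".
- **Population.** Safety analyses use the Full Analysis Population, which adds up to 50 lead-in subjects who are not randomised and all receive HEMOBLAST (Protocol 6.4.2 and 12.3.2.1).

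**The concern.** Operative time before the envelope is opened cannot differ by arm except by chance, yet its variability enters the standard error in full. The plan collects both clock times needed to remove it and analyses neither the interval between them nor any adjustment for the earlier part.

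The outcome matters to the sponsor's case: Protocol 4.2 names shorter operative time among the reasons why control of haemorrhage is important. If the arms differ through rescue treatment, re-bleeding or delayed closure, the planned contrast has less chance of showing it than the collected data allow. A wide interval around zero would also be weak reassurance for an outcome listed under safety.

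**Working it through.** Neither document gives an effect size, SD or power for operative time, so there is no planned figure to reproduce.

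**Inputs**
- 267 HEMOBLAST and 133 G+T subjects (Protocol 6.4.2).
- A two-sided 5% level, matching the planned 95% interval.
- 80% power, chosen here for comparison.
- Assumed SDs, none of them from the documents: 30, 60 or 90 min before randomisation (A) and 15, 30 or 45 min after it (B), with correlation 0 or 0.3.

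**Model.** Total time T = A + B, where assignment cannot affect A.
- SD(T) = √(SD_A² + SD_B² + 2·ρ·SD_A·SD_B)
- Detectable difference = (1.960 + 0.842) × SD × √(1/133 + 1/267) = 2.802 × 0.1061 × SD = 0.297 × SD

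In the middle case SD(T) = √(60² + 30²) = 67.1 min. The detectable difference is 19.9 min on T and 0.297 × 30 = 8.9 min on B.

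| SD before / after (min), correlation | SD total | Detectable, total time | Detectable, randomisation to closure | Variance ratio |
|---|---|---|---|---|
| 30 / 15, 0 | 33.5 | 10.0 | 4.5 | 5.0 |
| 30 / 45, 0 | 54.1 | 16.1 | 13.4 | 1.4 |
| 60 / 30, 0 | 67.1 | 19.9 | 8.9 | 5.0 |
| 90 / 15, 0.3 | 95.6 | 28.4 | 4.5 | 40.6 |
| 90 / 45, 0.3 | 112.0 | 33.3 | 13.4 | 6.2 |

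Over the whole grid the detectable difference is 10.0 to 33.3 min on total time and 4.5 to 13.4 min on the later interval. Power for a 5-minute effect is 6 to 29% against 18 to 88%. For a 10-minute effect it is 13 to 80% against 55 to 100%. If the trial stopped at 240 subjects, both detectable differences would grow by √(400/240) = 1.29 and their ratio would not change.

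**Bias check.** In 20,000 simulated trials with SDs of 60 and 30 min, zero correlation and a true 5-minute reduction, the mean estimate was −5.01 min (SE 7.1) from total time and −4.98 min (SE 3.2) from the later interval. The earlier time adds noise only.

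**Covariate version.** Putting A in the model for T leaves a residual SD of SD_B × √(1 − ρ²). That equals SD_B at zero correlation and 0.954 × SD_B at 0.3, so it does at least as well as analysing B.

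**Lead-ins.** If lead-ins are counted in the HEMOBLAST arm, they can form 50/317 = 16% of it, and the contrast is then not purely randomised. They add little precision: in the middle case the detectable difference on total time moves only from 19.9 to 19.4 min.

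**The case against.** The strongest reply is that nothing is wrong with the estimate and nothing depends on it. Among randomised subjects the total-time difference is unbiased. The plan reports an estimate with a 95% interval and sets no safety threshold or equivalence claim for operative time. Comparisons outside the fixed sequence are exploratory by Protocol 12.2.4. All of this stands, and it limits the weight of the point. It does not justify leaving out an interval whose two clock times are already collected.

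Four stronger readings are tempting, and the documents do not support them.
- **Total operative time cannot show a device effect.** It can, if the effect is large enough. Power for 10 minutes reaches 80% at the favourable end of the assumed SDs.
- **Most of the operation precedes randomisation, so a null result is nearly certain.** The sequence of events suggests a sizeable earlier part, most clearly in cardiothoracic cases. However, no section gives the share, and nothing places the site early or late in abdominal or orthopaedic surgery.
- **A preparation-time advantage is being hidden.** For randomised subjects Protocol 6.4.2 says: "At the start of each surgical procedure, a single HEMOBLAST™ device and a single G+T device will both be prepared". A preparation difference therefore cannot appear in total time or in the later interval. It has its own secondary endpoint, and neither document says it should show in operative time.
- **Blood loss and transfusion should be split at randomisation as well.** That needs new data collection, and Protocol 4.3 already calls standardised measurement of total blood loss difficult.

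A fair limit on the benefit also stands. A 10-point difference in success at both 3 and 6 minutes moves the mean time on the 3/6/10-minute grid by 0.10 × 3 + 0.10 × 4 = 0.7 min. Even at an SD of 15 min the 95% half-width is 1.96 × 0.1061 × 15 = 3.1 min, so neither measure would detect it. The gain is for larger downstream effects: rescue after 10 minutes, re-bleeding, and use of the remaining product at other sites.

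**Conclusion.** The point holds as one of precision. The planned contrast carries avoidable variance from time before randomisation. Under the assumed SDs its variance is 1.4 to about 41 times that of the randomisation-to-closure interval, and 5 times in the middle case. The size rests wholly on those SDs and on the unknown split of the operation. The direction needs only that the earlier time varies and is not strongly negatively correlated with the later time.

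Two related matters need settling with it: operative time has no definition of its own, with two competing ones nearby, and non-randomised lead-ins may enter this comparison. The outcome is safety and exploratory, so the primary conclusion does not change.

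**What to change.** - In Protocol 5.4, 12.1.3 and 12.3.2.2 and SAP 10.6.2 and 10.8, make the between-arm comparison the interval from recorded time of randomisation to skin closure, in randomised subjects only, with the same regression adjusted for surgery type. Alternatively, keep total operative time as the response and add time from skin opening to randomisation as a covariate. State in advance which of the two is used.
- Keep total operative time as a descriptive summary by arm, with lead-ins shown separately.
- Define operative time once, and reconcile Protocol 6.4 with Protocol 17.

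The cost is a wording change to both documents and the loss of up to 50 lead-ins from this one comparison. Lead-ins have no randomisation time and no concurrent control. No new CRF field is needed.

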12.3.2 Analysis of Safety Outcomes

12.3.2.1 Analysis Population

Safety analyses will be conducted on the Full Analysis Population, defined as all subjects who were randomized into the study and received study intervention and all lead-in subjects.

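### The overall comparison of reoperation and bleeding complications names no sparse-event method; if the nearby robust Wald interval applies, it is too narrow when an arm has few or no events

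*Protocol*

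**What the plan says.** Protocol 12.3.2.2 and SAP 10.6.2 first list four continuous outcomes (blood loss, transfusion volume, operative time, hospital stay), to be compared by linear regression. They then state: "In all cases, the robust variance estimator will be used and a 95% Wald-based interval will be computed". The next sentence turns to reoperation (total and for bleeding) and post-surgery bleeding complications, whose overall comparison "will be made using a general linear model to estimate the difference in the probability of each outcome after stratified adjustment for surgery type".

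For comparisons inside a surgery type, the protocol says they "within each surgery type will be made using a two sample binomial test of proportions", and the SAP makes that test exact: "within each surgery type will be made using an exact two sample binomial test of proportions". The SAP adds two more provisions. One covers single proportions: "For binary endpoints, the proportion and corresponding 95% scored-based confidence interval will be computed". The other covers two event classes when none occur: "In the event that no UADEs or SADEs are observed, the upper bound of the 95% confidence interval will be based upon the exact binomial". Neither mentions the adjusted difference between arms.

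The safety population is "all subjects who were randomized into the study and received study intervention and all lead-in subjects" (Protocol 12.3.2.1). Protocol 6.4.2 states that "267 subjects will be randomized to receive HEMOBLAST", with 133 on G+T and at most 50 lead-ins, all on HEMOBLAST.

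**The concern.** In a linear model for a risk difference, the robust variance of each arm is driven by that arm's own observed events. An arm with no events contributes essentially nothing, as if its true rate were known to be zero. With at least two HEMOBLAST subjects per G+T subject, G+T is the arm more likely to be empty. The interval is then too short, and its errors fall mostly on the side of HEMOBLAST looking worse.

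Reoperation for bleeding is a named safety outcome (Protocol 12.1.3). At stake is a published 95% interval that excludes zero where an exact test on the same counts shows no evidence of a difference.

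**Working it through.** **Inputs.** From the documents: 267 HEMOBLAST, 133 G+T, up to 50 lead-ins, so 267 + 50 = 317 vs 133 in the safety population. If the trial stopped at the interim (160 and 80 treated, Protocol 12.4.1), the size would be at least 160 + 50 = 210 vs 80. Assumed: true event rates of 0.5 to 5%, equal in both arms, because neither document gives a rate.

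**The plan's own figure.** None is given for these comparisons. The only stated power, 80.1% for the primary test, reproduces as 80.0% with the futility boundary followed. It has no bearing on the safety intervals.

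**Step 1: one empty arm.** The Wald interval is d ± 1.96 × SE, with SE = √[p₁(1−p₁)/n₁ + p₂(1−p₂)/n₂]. For 4/317 vs 0/133:
- d = 1.262 percentage points; SE = √[0.01262 × 0.98738/317 + 0] = 0.627 points.
- Interval: 1.262 ± 1.229, that is +0.03 to +2.49, excluding zero.
- Fisher's exact p = 0.32; the Newcombe score interval is −1.65 to +3.20.
- The G+T term is zero, yet 0/133 is compatible with a rate up to 1 − 0.025^(1/133) = 2.7%.

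With fewer HEMOBLAST events the interval still has width and includes zero: 1/317 vs 0/133 gives −0.30 to +0.93, and 3/317 vs 0/133 gives −0.12 to +2.01. Fitting the model with three surgery-type strata to 2, 1 and 1 events vs none gives +0.03 to +2.50, so adjustment does not change the picture.

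**Step 2: both arms empty.** The Wald interval is 0 to 0; the Newcombe interval is −2.81 to +1.20. The probability is 0.99^450 = 1.1% at a 1% rate and 0.995^450 = 10.5% at 0.5%.

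**Step 3: how often zero is wrongly excluded.** Exact enumeration of two binomials, unpooled Wald interval. The nominal rate is 2.5% on each side.

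| Assumed rate | 317 vs 133: HEMOBLAST worse / better | 267 vs 133: worse / better | 210 vs 80: worse |
|---|---|---|---|
| 0.5% | 3.9% / 0.1% | 2.4% / 0.1% | 1.5% |
| 1% | 10.3% / 0.4% | 7.4% / 0.6% | 7.2% |
| 2% | 7.1% / 0.8% | 7.1% / 1.1% | 12.2% |
| 3% | 5.2% / 1.1% | 5.6% / 1.3% | 8.9% |
| 5% | 4.6% / 1.3% | 4.1% / 1.6% | 6.0% |

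The 1% row can be traced by hand. G+T is empty with probability 0.99^133 = 26.3%, and four or more of 317 HEMOBLAST subjects have an event with probability 39.1%. The product is 10.3%, essentially the whole error.

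A simulation of the stratified linear model with robust variance agrees at 317 vs 133: 3.9, 10.2, 7.0, 5.4 and 4.6%. The HC3 small-sample correction leaves these almost unchanged.

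**Step 4: the other reading.** With ordinary model-based variance in the same model, false harm falls to between 0.0 and 2.1% and false benefit rises to between 2.9 and 4.6%.

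**Step 5: alternatives at 317 vs 133** (rates 0.5, 1, 2, 3, 5%).
- Pooled score test: worse 0.0, 0.1, 1.4, 1.9, 2.1%; better 4.0, 4.8, 3.6, 2.9, 3.0%.
- Fisher's exact test: worse 0.0, 0.0, 0.8, 1.3, 1.6%; better 0.8, 1.5, 1.9, 2.3, 2.3%.

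**The case against.** **The plan may not attach robust Wald to these outcomes.** The sentence closes the list of continuous means, and the binary outcomes follow under a differently named model. This stands as a real ambiguity. The Wald reading is still plausible: it is the only variance and interval named for a between-arm safety difference, and Protocol 12.3.1.2 pairs a general linear model with Wald intervals for 3-minute hemostasis. If it does not apply, no interval is specified at all.

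**A reader might infer that the method always signals false harm.** The documents do not support that. The direction depends on the unstated variance, and at a 0.5% rate with 267 vs 133 the false-harm rate is 2.4%, within nominal. The marked inflation lies at about 1 to 3%. Rarity is itself an assumption: Protocol 13.2 lists hemorrhage among events above 1% in a trial of another hemostat, with no upper figure.

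**A reader might also infer that an empty arm leaves the interval without width.** It does not; that needs both arms empty.

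**The SAP already deals with sparse data.** In part it does, by score intervals for single proportions, exact tests within surgery type and an exact bound for zero UADEs or SADEs. A score interval for 0/133 beside the difference would warn a careful reader. None of these provisions covers the overall adjusted difference.

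**Score methods are not perfect either.** True: at low rates the score test's errors lean toward false benefit, much as model-based variance does. Its total error at 317 vs 133 is nevertheless 4.0 to 5.1%, against 10.3 + 0.4 = 10.7% for robust Wald at a 1% rate. The exact test stays below 2.5% on both sides.

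**Conclusion.** The concern holds conditionally and is minor. If robust variance with a Wald interval is meant for the binary safety outcomes, the chance of wrongly showing HEMOBLAST worse reaches about four times nominal (10.3% against 2.5%) in the planned safety population at a 1% event rate, and falls to 4.6% at 5%. If model-based variance is meant, total error stays near 5% but leans toward false benefit. Two readings that err in opposite directions are reason enough to settle the method.

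The size rests on assumed equal event rates, on all 50 lead-ins being enrolled, and on the reading of one sentence. It would go too far to say that the trial's conclusions are at risk. Success is defined by 6-minute non-inferiority (Protocol 12.1.4), comparisons outside the fixed sequence are exploratory (Protocol 12.2.4, SAP 10.10), and there is no safety hypothesis or safety success criterion.

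**What to change.** In Protocol 12.3.2.2 and SAP 10.6.2, for the overall adjusted difference in reoperation, reoperation for bleeding and bleeding complications:

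- Replace the linear-model interval with a score interval stratified by surgery type, for example Miettinen-Nurminen, or another named method that behaves properly with few or no events.
- Use an exact test overall, as the SAP already does within surgery type.
- Limit the robust-variance sentence explicitly to the continuous outcomes, and keep the linear model for those.

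The cost is a few lines of text and standard software. Intervals for rare events will be wider: for 4/317 vs 0/133, about 4.9 points (Newcombe, 3.20 + 1.65) instead of 2.5 (2.49 − 0.03). That width reflects what the data can show.
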